#### 4.2.5. Statistical Analysis

Survival from date of surgery for LDLT versus DDLT transplant will be compared using
Cox regression, adjusted for prognostic variables. The distributions of time from
transplant to rejection episode, or graft failure, between LDLT and DDLT transplant will
be similarly compared.

751

752 Initial analysis of LDLT recipient post-operative complications will be descriptive. We 753 will report the proportions of donors with complications such as bile leak, primary non-754 function, graft failure, pneumonia, and urinary tract infection, as well as any complication 755 requiring hospital admission, re-operation, or other intervention. Confidence intervals 756 will be included with all estimates. We will also report follow-up outcomes including 757 wound healing, pain medications, blood laboratory values, and the proportion of patients 758 who returned to work/school. Some attempt will be made to correlate complications with 759 patient characteristics and operative procedures, but any such analyses will be limited by

760 the quality of available data.

761 In addition, a comparison of LDLT complications with complications following DDLT

will be made. Depending on the type of complication (event occurrence, time to event, or

continuous outcome), a comparison of the events between LDLT and DDLT transplants

will be made using logistic regression, Cox regression, or ordinary regression,

- respectively, each adjusted for other predictive variables as needed.
- 766

Resource utilization, particularly hospitalization (number of hospitalizations and number
of hospital days) will be compared for those with and without LDLT using a repeated
measures generalized linear model analysis starting at the time of donor evaluation. In
addition, a comparison of hospitalization outcomes after LDLT versus DDLT will be

- made. Quality of life outcomes will be subscale scores calculated as weighted sums of
- ordinal variables, and can be analyzed as continuous variables. For comparing post transplant quality of life for LDLT versus DDLT, we will use repeated measures
- regression. Treatment differences as well as treatment by time interactions will be tested.
- 775

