1149 outcome of 42 LDLT HCV patients was compared to 86 HCV patients undergoing 1150 DDLT. Mean AST and ALT were higher at each follow-up interval reaching statistical 1151 significance at months 1 and 3 for AST and month 1 for ALT. The percentage of patients 1152 with aminotransferase > 100 IU/or bilirubin > 2 mg/dl was higher at each time point for 1153 live donor liver transplant recipients. The time to histologic recurrence was significantly 1154 shorter in live donor recipients (3.5 months) vs. DDLT recipients (6.7 months), (p=0.01) 1155 but protocol biopsies were not performed. While these results suggest that HCV may 1156 recur earlier and be associated with higher serum aminotransferase levels in live donor 1157 liver transplant patients compared to DDLT recipients, the longer term outcomes (risk of 1158 progressive fibrosis and graft loss) are unknown. The current study will examine the rate 1159 and severity of HCV disease in a large prospective cohort of live donor and DDLT 1160 recipients over a 3-year period. Liver biopsies obtained at 3 months and annually will be 1161 compared between groups to assess differences in liver fibrosis and total 1162 necroinflammatory activity, controlling for other factors known to affect disease

- 1163 progression (e.g. donor age, acute rejection episodes, baseline viral level).
- 1164

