#### 1183 **Primary Endpoint**

- Proportion of patients with one of the following four endpoints indicative of "progressive" disease:
  - a. Ishak fibrosis score of  $\geq 3$  (some bridging fibrosis)
  - b. Ishak fibrosis score of  $\geq 2$  plus total bilirubin > 5.0 mg/dL
- 1188c. Ishak fibrosis score of  $\geq 2$  plus Knodell score (necroinflammatory indices)1189 $\geq 9$ 
  - d. Diagnosis of cholestatic hepatitis
- 1192 Additional causes of liver test elevation must be excluded. Specifically, there must be:
  - e. Absence of rejection (acute and chronic)
    - f. Absence of biliary disease

1195	g. Sepsis
1196	
1197	Secondary Endpoints
1198	1. Rate of fibrosis progression (Ishak fibrosis score) – change in fibrosis score per
1199	year
1200	2. Total and necroinflammatory scores at 3 months, 1 year, 2 years and 3 years
1201	(Knodell score)
1202	3. Time to recurrence of disease determined by proportion of patients with
1203	histological evidence of recurrent HCV at 3 and 12 months
1204	4. Viral level at day 7 and months 1, 3, and 12, 24 and 36– comparison of LD and
1205	DDLT recipients and prediction of post-LT disease progression.
1206	5. Proportion with cholestatic hepatitis
1207	6. Graft and patient survival
1208	
1209	4.5.2. Participant Selection
1210	See Section 4. for general eligibility criteria, and Section 4.2.2 for further details on
1211	selection of contemporaneous controls.
1212	4.5.3. Data Elements
1213	Potential Recipients positive for HCV
1214	1. HCV at enrollment
1215	2. HCV survey
1216	
1217	Recipients positive for HCV
1218	1. HCV intraoperative sample collection
1219	2. HCV at Transplant
1220	3. HCV Post-operative Recurrence and Rx data
1221	4. Liver biopsy and histology data
1222	
1223	Histological Evaluation:
1224	Local pathologists will use a standardized form for scoring all liver biopsies on HCV
1225	study participants performed after the first 4 weeks post-transplantation. The Knodell
1226	system (See Appendix R) will be used. To be an evaluable biopsy, in terms of HCV-
1227	related endpoints, there must be an absence of other concurrent conditions such as acute
1228	rejection, biliary obstruction and CMV hepatitis. Both protocol liver biopsies (month 3
1229	and annually) and non-protocol biopsies will be scored for evidence of HCV recurrence.
1230	4.5.4. Sample Size and Power Calculations
1231	We estimate the total number of transplant patients available (based on the recent survey

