## 4.5.5. 4.5.5 Statistical Analysis

The primary objective is to compare HCV progression probabilities in LDLT versus DDLT, where HCV progression is defined above. This comparison will be tested using logistic regression, with HCV progression (yes/no) at a given time point as the outcome variable, and LDLT versus DDLT as the covariate of interest. This comparison will be adjusted for other variables associated with HCV progression. If HCV progression is evaluated at regular points over time, then discrete time survival analysis will be used to compare the time until HCV progression in the two groups.

1262

1263 Secondary objectives will involve several analyses. First, both the rate of fibrosis 1264 progression (change in Ishak score over time) and change in the necroinflammatory score 1265 (Knodell score) will be analyzed using repeated measures regression. A difference in 1266 slopes of the Ishak or Knodell scores over time for LDLT and DDLT will be tested with 1267 an interaction term between LDLT/DDLT and follow-up time. Second, the proportion of 1268 patients with histologic evidence of recurrent HCV at 3 months and 1 year after LDLT 1269 versus DDLT will be compared using logistic regression. This analysis will parallel the 1270 analysis for the primary objective described above. Because recurrent disease occurs 1271 prior to progressive disease, these two analyses will not be independent. Third, analysis 1272 of viral level at day 7 and months 1, 3, 6, and 12 will be performed using repeated 1273 measures regression, with the primary comparison between LDLT and DDLT. 1274 Differences in the pattern of viral levels over time will be tested using a time by 1275 LDLT/DDLT interaction. As a second step, HCV disease severity will be added to the 1276 model to see if viral level is significantly predicted by disease severity. Fourth, the 1277 incidence of cholestatic hepatitis in LDLT and DDLT will be compared using logistic 1278 regression, adjusted for any other prognostic factors. Finally, graft and patient survival 1279 will be analyzed using Kaplan-Meier estimators, logrank tests comparing LDLT and 1280 DDLT, and Cox regression to compare groups adjusted for other variables.

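### The Knodell endpoint is the score at four visits, but the only test named for it is a slope difference, which cannot detect an LDLT–DDLT difference already present at month 3 and constant afterwards

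*Protocol*

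**What the plan says.** The Secondary Endpoints list in 4.5.1 separates two histological quantities. Item 1 is a rate: "Rate of fibrosis progression (Ishak fibrosis score"), defined as change per year. Item 2 is a level at fixed times: "Total and necroinflammatory scores at 3 months, 1 year, 2 years and 3 years", scored by Knodell. The background in 4.5 also says that the 3-month and annual biopsies will be compared between groups for fibrosis and necroinflammatory activity.

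Section 4.5.5 handles both items together. It says that fibrosis progression "and change in the necroinflammatory score" will be analysed by repeated measures regression, and that a difference in "slopes of the Ishak or Knodell scores over time for LDLT and DDLT will be tested with" "an interaction term between LDLT/DDLT and follow-up time". No group effect and no per-visit contrast is named for Knodell.

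Two other repeated measures analyses in the protocol are specified differently. For viral level, the same section plans repeated "measures regression, with the primary comparison between LDLT and DDLT", with the time interaction tested in addition. For recipient quality of life, 4.2.5 says: "Treatment differences as well as treatment by time interactions will be tested".

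Protocol biopsies after transplant fall at month 3 and years 1, 2 and 3 (Section 4 and Appendix A). Only biopsies after the first 4 weeks are scored for HCV (4.5.3). The preliminary data in 4.5 report that time to histologic recurrence was "shorter in live donor recipients (3.5 months) vs. DDLT recipients (6.7 months), (p=0.01").

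**The concern.** A slope interaction asks whether the two groups' scores diverge or converge after the first measurement. Endpoint 2 asks how high the scores are at each visit. Any difference already present at month 3 goes into the group term, for which no test is named. The protocol itself cites data in which LDLT disease appears early, so a difference by month 3 is a realistic possibility.

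Two things are at stake. A persistent difference in necroinflammatory activity could go undetected by the one test named for it. And if DDLT recipients start lower and catch up, their slope is the steeper one, so the test could be read as slower progression after LDLT although LDLT scores were never the better ones.

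**Working it through.** **Inputs from the protocol.** 108 LDLT and 107 DDLT recipients with HCV, two-sided 0.05 (4.5.4); biopsies at t = 0.25, 1, 2 and 3 years; recurrence at 3.5 v 6.7 months (4.5). **Assumed, because the protocol gives none:** Knodell SD, within-patient correlation and course over time.

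**1. The plan's own slope figure.** Section 4.5.4 states 82% power for a fibrosis-rate difference of 0.10 per year with SD 0.25. SE = 0.25 × √(1/108 + 1/107) = 0.25 × √0.018605 = 0.0341. Then 0.10/0.0341 = 2.93, and power = Φ(2.93 − 1.96) = 83.5% (83.1% with the t distribution). This agrees within 2 points and is not in dispute. It concerns Ishak; no power is given for Knodell.

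**2. What the interaction measures.** The mean of t is 1.5625. The centred times are −1.3125, −0.5625, 0.4375 and 1.4375, with Sxx = 4.297. With LDLT minus DDLT differences D at the four visits:

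slope difference = Σ(t − 1.5625) × D / 4.297

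The centred times sum to zero, so a constant D gives exactly zero, whatever its size.

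**3. A constant excess of 1.5 points** (SD 3, correlation ρ = 0.5):

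- Interaction: slope difference 0, so it rejects in 5.0%, the significance level.
- Average level: SE = √(9 × (0.5 + 0.5/4) × 0.018605) = 0.3235; z = 1.5/0.3235 = 4.64; power 99.6%.
- Month-3 contrast: SE = 3 × √0.018605 = 0.409; z = 3.67; power 95.6%.
- Joint 4-df test: noncentrality = 4 × 1.5² / (9 × (1 + 3 × 0.5) × 0.018605) = 21.5; power 97.5%.

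Over SD 2 to 4 and ρ 0.3 to 0.7, the joint test has 70% to 100% power. The interaction stays at 5% throughout.

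**4. The sign under early onset with catch-up.** Take 3.5 and 6.7 months as medians of exponential recurrence times, with a score of 0 before recurrence and 5 from recurrence on. The mean score at visit t (in months) is 5 × (1 − exp(−ln2 × t/median)):

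| | 3 mo | 12 mo | 24 mo | 36 mo | Slope per year |
|---|---|---|---|---|---|
| LDLT | 2.2 | 4.5 | 5.0 | 5.0 | 0.90 |
| DDLT | 1.3 | 3.6 | 4.6 | 4.9 | 1.23 |

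LDLT is higher at every visit, yet its slope is lower by 0.33 per year.

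**5. How often that would be significant.** Simulated per-patient slopes compared by t-test, 108 v 107, between-patient SD 2, within-patient SD 1.5. Rates are good to about two points.

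| Course after recurrence | Plateau LDLT v DDLT | Significant: LDLT slower | Significant: LDLT faster |
|---|---|---|---|
| Instant | 5 v 5 | 59% | about 0% |
| Rise over 6 months | 5 v 5 | 17% | about 0% |
| Rise over 1 year | 5 v 5 | 3% | about 1% |
| Instant | 6 v 5 | 14% | about 0% |
| Rise over 6 months | 6 v 5 | 0% | 30% |
| Rise over 1 year | 6 v 5 | 0% | 79% |

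Step 3 needs no assumption about the course beyond a constant difference. The result of step 5 depends almost entirely on the assumed course.

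**The case against.** The strongest reply has four parts.

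- **Early disease is tested elsewhere.** Section 4.5.5 compares histologic recurrence at 3 months and 1 year by logistic regression. The primary composite, one arm of which is Knodell 9 or more with Ishak 2 or more, is compared at a given time point. This stands. A reader might infer that earlier LDLT disease would go unseen or appear only as slower progression; the protocol does not support that. But both analyses are yes/no, and neither compares Knodell scores.
- **Sign reversal is not the protocol's expectation.** The background in 4.5 describes LDLT injury as both earlier and more severe, and calls longer-term outcomes unknown. With a higher LDLT plateau and a gradual rise, the slope test points the right way. The recurrence times come from a study without protocol biopsies and are not labelled as means or medians. This stands too. A reader might infer that the test will tend to favour LDLT wrongly; step 5 shows that only particular courses give this.
- **A repeated measures model normally contains a group term, and visit contrasts may be left to a statistical analysis plan.** This stands in part: the text does not say that only slopes will be tested. But the protocol does name a test for Knodell, and it is the wrong one for endpoint 2. The group comparison is written out for viral level and quality of life, so its absence here does not read as shorthand.
- **Section 3.5 lists no objective for the numeric Knodell score at each visit.** True, though it does ask about histological severity at one year, and 4.5.1 lists the scores as an endpoint.

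One further limit: unscheduled biopsies after week 4 are also scored, so a few values may precede month 3. They do not give a systematic baseline.

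**Conclusion.** The mismatch is in the text: endpoint 2 is a level at four visits, and the only test named for it is a difference in slopes. The firm consequence is that a level difference present at month 3 and constant afterwards cannot be detected by the named test. Rejection stays at 5%, against about 97% for a joint visit test of a 1.5-point excess at SD 3 and correlation 0.5, both assumed.

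A significant result in favour of LDLT when its scores are higher is possible but conditional: about 59%, 17% or 3% with equal plateaus, and 0% with a higher LDLT plateau and a 1-year rise. It should be presented as one scenario. Nor does the point extend to Ishak, where the endpoint is itself a yearly rate and a slope test fits. For one secondary endpoint of a secondary aim, this is a correction that should be made, not a threat to the main comparison.

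**What to change.** In 4.5.5, separate the two scores. For Knodell, fit the repeated measures model with visit (3, 12, 24 and 36 months) as a categorical factor. Report the LDLT minus DDLT difference in mean score with its CI at each visit, and make the joint test of group and group-by-visit the test for endpoint 2. Keep the slope interaction as a supplement, in the way the same section does for viral level. Leave the slope test as it is for the Ishak rate.

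The cost is a change of wording and a few extra degrees of freedom (a 4-df test in place of 1 df). Data, visits and software are unchanged.

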162	4.	To determine if HCV viral level at day 7 and months 1, 3, 12, 24 and 36
163		months differ in LDLT and DDLT recipients, and whether viral level is
164	-	predictive of disease severity.
165	5.	J I I C C
166		HCV patients who undergo LDLT as compared to DDLT transplant and to
167		correlate this frequency of treatment of rejection to aggressive recurrence of
168	ſ	HCV as defined histologically.
169	0.	To compare biochemical markers of disease activity (ALT/AST/total
170	7	bilirubin) at 3 and 12 months and annually in LDLT and DDLT.
171	7.	To determine if cholestatic hepatitis in transplanted patients with HCV occurs
172 173	0	in a higher proportion of LDLT as compared to DDLT recipients.
	8.	
174		DDLT recipients.
175		
176	3.6. Se	econdary Aim 2: Recurrence of HCC for DDLT versus LDLT.
177		
178	Primary O	bjectives
170	1	To determine if I DI T is appreciated with deepended doth on writing list from

- To determine if LDLT is associated with decreased death on waiting list from progressive tumor growth versus DDLT.
- 181 2. Assess comparative HCC recurrence following LDLT or DDLT.

Revised Cohort Protocol 031006

182 183 184 185	
 
Compare long-term survival and disease free survival in patients who undergo LDLT or DDLT.
 
Secondary Objectives
 

186 187 188 189 190	
 
Determine if LDLT recipients require a reduced number of palliative ablative procedures to control HCC when compared to those who wait for DDLT.
 
Compare rates of surgical and post-operative complication in HCC recipients of LDLT and DDLT.
 

190 191 192	3.7. Secondary Aim 3: To systematically characterize liver regeneration and function in donors and recipients.
193 194 195 196	Donors and recipients enrolled in the cohort study will be evaluated for evidence of recovery of liver mass and function following the surgical procedures (partial transplantation for recipients of LDLT, and partial hepatectomy for donors).
197 198 199 200 201	In the cohort protocol all donors and recipients of LDLT will undergo standardized assessments of liver volume and function to characterize the rate of restoration of the liver. In the recipient, in which the relative size of the graft will vary based on the unique donor/recipient combinations, the large sample provided in the study will permit us to correlate graft function with a number of donor and recipient parameters.

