468 469 470 471 472 473 474 475 476 477	
 
Physical examination: including weight, blood pressure, etc.
 
Routine laboratory assessment: blood will be drawn to obtain values for the following tests: multichannel automated liver function tests, serum sodium, albumin, AFP, creatinine, and coagulation panels
 
Blood sample for NIDDK Biosample Repository
 
Quality of life interval assessments at 3, 6, and 12 months and annually thereafter
 
Liver MRI/contrast CT at Month 3 only.
 
Recipients of a DDLT from an HCV-antibody positive donor must have HCV genotyping done at 3 months post-transplant
 

478 479	Post-transplant Interval Assessments – HCV-infected Recipients:
480	In addition to the assessments listed above, HCV-infected recipients will undergo the following assessments at the following time points:

483	• Week 1, Month 1, Month 3, Year 1, 2, and 3: HCV RNA quantitative or qualitative
484	analysis
485	• Month 3, Year 1, 2 and 3: Liver biopsy
486	• Month 3, Year 1, 2 and 3: Tissue sample for NIDDK Biosample Repository
487	
488	Post-transplant Interval Assessments – Subjects with HCC:
489	
490	In addition to the assessments listed above for all recipients, recipients with HCC will
491	undergo the following assessments at Months 6, 12, 18 and 24:
492	
493	• Serum AFP (at month 18 in addition to AFP's done at interval assessments for all
494	recipients)
495	• Abdominal MRI/contrast CT: at months 6, 12 and 24 only.
496	
497	Subjects Showing Signs and Symptoms of Allograft Rejection:
498	
499	Subjects showing signs and symptoms of allograft rejection will undergo a liver biopsy
500	with analysis to confirm the diagnosis of rejection. A biopsy will be performed to
501	confirm each rejection episode. A tissue sample from these biopsies will also be sent for
502	storage at the NIDDK Biosample Repository.
503	
504	Post-Donation Assessments – Donors:
505	
506	The following assessments will be performed for donors at Week 1, and Months 1, 3, and
507	12, and annually thereafter until the study is complete or the donor reaches a study
508	endpoint or is lost to follow-up:
509	
510	• Routine laboratory assessment: blood will be drawn to obtain values for the
511	following tests: multichannel automated liver function tests, albumin, creatinine,
512	coagulation panels, white blood cell count, hemoglobin, ferritin, platelets, BUN
513	Blood sample for NIDDK Biosample Repository
514	• Liver MRI/contrast CT at month 3 only

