#### 2136 APPENDICES

	Pre Transplant         Transplant           Period         Hospitalization         Post Transplant Follow-up Period           Quarterly from         Post Transplant Follow-up Period													
Visit Type	Enrollment	Transplant OP Day 0	PTD1	PTW1	PTW2	PTM1	PTM3	PTM6	PTM12	PTM18	PTM24	PTM36	PTM48	PTM60
Recipients														
Allograft Biopsy		ALL					HCV		HCV		HCV	HCV		
HLA Typing	ALL (ONCE)													
HCV Genotyping	HCV													
HCV RNA quant/qual	HCV	HCV		HCV		HCV	HCV		HCV		HCV	HCV		
Chest CT	HCC													
Bone Scan	HCC													
Abdominal MRI/Contrast	HCC							НСС	HCC		HCC			
HCC Explant Histologic Analysis		HCC						1100	1100		100			
AFP	ALL	ALL					ALL	ALL	ALL	HCC	ALL	ALL	ALL	ALL
Explant biopsy		ALL												
Liver MRI							ALL							
LFT's	ALL	ALL		ALL	ALL	ALL	ALL	ALL	ALL		ALL	ALL	ALL	ALL
Albumin	ALL	ALL		ALL	ALL	ALL	ALL	ALL	ALL		ALL	ALL	ALL	ALL
INR	ALL	ALL		ALL	ALL	ALL	ALL	ALL	ALL		ALL	ALL	ALL	ALL
Serum creatinine	ALL	ALL		ALL	ALL	ALL	ALL	ALL	ALL		ALL	ALL	ALL	ALL
Serum Sodium	ALL	ALL		ALL	ALL	ALL	ALL	ALL	ALL		ALL	ALL	ALL	ALL
PT/PTT	ALL	ALL		ALL	ALL	ALL	ALL	ALL	ALL		ALL	ALL	ALL	ALL
Blood for Sample														
Repository	ALL	ALL	ALL	ALL	ALL	ALL	ALL	ALL	ALL		ALL	ALL	ALL	ALL
Tissue for Sample Repository		ALL					HCV		HCV		HCV	HCV		
Cells for Genetics	ALL (at Enrollment													
Repository	only)													
QOL Assessments	ALL						ALL		ALL		ALL	ALL	ALL	ALL

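### The HCV viral-level analysis in Section 4.5.5 reverses the prediction its objective asks for, and its visit list does not match the endpoint or the HCV RNA schedule

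*Protocol*

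**What the plan says.** Secondary objective 4 of Secondary Aim 1 (Protocol 3.5) begins "To determine if HCV viral level at day 7 and months 1, 3, 12, 24 and 36" and continues "months differ in LDLT and DDLT recipients, and whether viral level is" "predictive of disease severity". It therefore has two parts: a comparison of levels between graft types, and a question about prediction in which viral level is the predictor.

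Secondary endpoint 4 (Section 4.5.1) gives the same visits, "Viral level at day 7 and months 1, 3, and 12, 24 and 36", and again pairs the group comparison with use of the level to predict progression after transplant.

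The post-transplant assessment list for HCV-infected recipients (Section 4) schedules "Week 1, Month 1, Month 3, Year 1, 2, and 3: HCV RNA quantitative or qualitative" analysis. In Appendix A, the row "HCV RNA quant/qual" marks the same post-transplant visits and is blank at month 6.

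Section 4.5.5 says that analysis "of viral level at day 7 and months 1, 3, 6, and 12 will be performed using repeated" measures regression, with LDLT versus DDLT as the main comparison and a time-by-group interaction. As a second step, severity is added to that "model to see if viral level is significantly predicted by disease severity".

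**The concern.** The analysis section disagrees with the objective, the endpoint and the schedule, which agree with one another. The disagreement concerns both the direction of the model and the visits.

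If 4.5.5 is followed literally, the prediction question gets a coefficient for viral level given severity. The question asked is how progression depends on an earlier level. The analysis would also expect data at a visit with no planned assay and stop at month 12, although levels are collected for two further years.

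The later period matters on the protocol's own planning figures. Section 4.5.4 assumes that 10% of DDLT patients reach the composite endpoint at 1 year and 50% at 3 years.

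**Working it through.** **Visits, side by side** (week 1 = day 7; years 1, 2, 3 = months 12, 24, 36)

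| Source | d7 | m1 | m3 | m6 | m12 | m24 | m36 |
|---|---|---|---|---|---|---|---|
| Objective 4 (3.5) | yes | yes | yes | no | yes | yes | yes |
| Secondary endpoint 4 (4.5.1) | yes | yes | yes | no | yes | yes | yes |
| Post-transplant HCV list (Section 4) | yes | yes | yes | no | yes | yes | yes |
| Appendix A, HCV RNA row | yes | yes | yes | no | yes | yes | yes |
| Analysis (4.5.5) | yes | yes | yes | yes | yes | no | no |

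**Counts**

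- Scheduled and in the endpoint but not analysed: months 24 and 36, 2/6 = 33%.
- Analysed but with no scheduled assay: month 6, 1/5 = 20%.
- Common to both: day 7 and months 1, 3 and 12, which is 4 visits.
- Ceiling on unused values: Section 4.5.4 expects 108 LDLT and 107 DDLT patients with HCV, so (108 + 107) × 2 = 430. This assumes every patient is alive with the graft in place, followed and sampled at both visits.
- Share of progression after month 12, reading the DDLT planning figures as cumulative: (50 − 10)/50 = 80% of the progression expected by year 3.

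**Direction**

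- Objective and endpoint: viral level is the predictor; severity or progression is the outcome.
- Section 4.5.5, second step: severity is the predictor; viral level is the outcome.

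For a simple unadjusted association the choice of outcome would not affect the test. Here the model is a repeated measures regression with group and time terms. With viral level as outcome, it gives no estimate of how an earlier level changes the chance of later progression.

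**Where severity is available.** Protocol biopsies fall at month 3 and years 1, 2 and 3, and the standardised scoring form applies to biopsies after the first 4 weeks (Section 4.5.3). Of the four visits common to analysis and schedule, planned histology exists at months 3 and 12 but not at day 7 or month 1. A clinically indicated biopsy could fall earlier, but none is planned. The early levels, the natural candidates for prediction, are thus where a concurrent severity term is least available.

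**Is the question answered elsewhere?** The introduction to Section 4.5 names baseline viral level among the factors controlled for in the histology comparison. The primary HCV model in 4.5.5 adjusts for other variables associated with progression, without naming them. Neither states a test of post-transplant level.

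**Assay.** The visit lists and Appendix A accept a quantitative or a qualitative HCV RNA result. A qualitative result gives detected or not detected, so a visit tested only that way has no value for a viral-level model. How often this would happen is not stated.

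**The case against.** The strongest reply is that most of the objective survives. The group comparison is what 4.5.5 calls primary. It runs in the right direction and has scheduled data at four visits named in the endpoint. That stands: a reader might infer that objective 4 cannot be answered at all, and the documents do not support this.

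A reader might also infer that the model conditions on the future, with later histology explaining earlier viral load. Section 4.5.5 does not date the severity term. Since biopsies and viral levels coincide at month 3 and year 1, a concurrent, time-varying covariate is an equally fair reading. It would test association between level and severity, but still not prediction of later progression.

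Three further limits stand. A month 6 visit exists and recipients give repository blood then, so what is missing is a scheduled assay, not a sample. The choice of assay is worded test by test, so it does not follow that a center using qualitative assays contributes nothing. Section 4.5.1 allows antiviral therapy once disease reaches a defined severity, so levels at months 24 and 36 would increasingly be on-treatment values, selected by severity. Adding those visits without allowing for this would create a new problem.

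Finally, this is one secondary objective within a secondary aim, with no power statement of its own.

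**Conclusion.** The point holds as two contradictions. First, the second step in 4.5.5 runs opposite to objective 4 and secondary endpoint 4, and no other stated analysis tests post-transplant viral level as a predictor. Second, the visit list includes one visit without a scheduled assay and omits two of the six scheduled endpoint visits. The 430 values are an upper bound; the real number depends on survival, graft loss and retention, which the protocol does not project for this subset.

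The primary HCV histology endpoint and its power calculation are unaffected. The assay wording is a related inconsistency of unknown size. These conclusions rest on reading 4.5.5 as the intended analysis. Specifics such as outcome scale or model form may properly be left to a statistical analysis plan, but the direction and the visit list are stated in the protocol and conflict within it.

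**What to change.** In Section 4.5.5:

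1. List the viral-level visits as week 1 and months 1, 3, 12, 24 and 36, and delete month 6.
2. Replace the second step with a model of later HCV progression or fibrosis on earlier viral level. The model form and the landmark visit can be left to the statistical analysis plan.
3. State how antiviral treatment started before the later visits is taken into account in analyses using those levels.

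In the visit lists and Appendix A, reconcile the permission for a qualitative assay with an endpoint that is a level, for example by requiring a quantitative result at the visits that feed this endpoint. This is best settled prospectively. Repository blood is drawn at those visits and might allow a level to be recovered, but no such assay is planned.

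The first three changes cost only wording, since the six visits are already scheduled. The fourth may add a modest laboratory cost where a qualitative assay would otherwise have been used. No visit or treatment rule changes.
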